6.0 INTERVENTION

6.1 Study Day 1

- Second urine pregnancy test will be obtained by the study coordinator(s) for women of child-bearing potential. Pregnancy test results will be obtained and recorded by the study coordinator(s) immediately prior to study drug administration.
- Assess noise exposure compliance
- Assess for medication compliance/change
- Study Drug to be dispensed and recorded at morning and evening meals by the on-site study coordinator(s).

6.2 Study Days 2-18

- Assess for Adverse Events and complete AE Log
- Assess for medication compliance/change

- Assess for hearing protection compliance (Days 4-14 only)
- Study Drug to be dispensed and recorded at morning and evening meals by on-site study coordinator(s).
- Urine and blood samples will be collected while on treatment (during second week). Two additional samples of blood (20-25 ml) will be collected for chemistry tests, complete blood counts, and tests of liver function, and homocysteine level. Urine sample will be collected for urinalysis.

6.3 Study Days 29-32

At the end of the study, Study Days 29-32, subjects will return to complete post-study audiologic exams including pure-tone thresholds, screening tympanometry and tinnitus questionnaires. Subjects will be contacted by telephone or text message to remind them to avoid noise exposure for at least 24 hours prior to the audiological assessments (hearing tests) by the on-site study coordinator(s). Concomitant medication usage, adverse events and study procedures/ compliance will be reviewed and confirmed.

- Urine and blood samples will also be collected post treatment. Two additional samples of blood (20-25 ml) will be collected for chemistry tests, complete blood counts, and tests of liver function, and homocysteine level. Urine sample will be collected for urinalysis.

7.0 STUDY DRUG

Study drug will be shipped to the study site as blind-labeled, ready-to-use bottles containing D-methionine or placebo ready for administration.

7.1 Formulation, Packaging, and Labeling

Study drug and Placebo will be formulated, shipped and packaged by KP Pharmaceutical Technology (KPT), Bloomington, Indiana. The suspension is provided in small vials at a D-methionine concentration of 200 mg/mL. Study drug will be prepared and labeled for each subject in individual vials by KPT. The formulation is comprised of the common excipients polysorbate 80 (Tween), methylparaben, propylparaben, sorbitol and orange extract added for taste and palatability. The formulation is stable when stored at controlled room temperature for at least 3 months. For longer storage, suspension must be maintained under refrigeration.

The placebo is flavor and color matched and delivered in equivalent volume to the active compound. The test drug D-methionine and the placebo are both formulated according to Good Manufacturing Practice (GMP) standards by KP Pharmaceutical Technology (KPT) as an oral suspension. KPT prepared these same formulations for the ex-US clinical trials for prevention of radiation-induced oral mucositis and cisplatin-induced hearing loss.

7.2 Dispensing Study Drug

Study drug will be dispensed by MACH Pharmacy to on-site study coordinator(s), who are qualified medical personnel (RN or LPN). The study drug will be distributed to the study participants as labeled in accordance with the study protocol. CPT [name]. will supervise the activities of the study coordinator(s) and audiologists.

The formulated drug product (D-methionine) will be provided for clinical use as an oral suspension. Each dose will be packaged in individually labeled vials. Each vial will have a subject identification number on the label (Section 15.1 Master Label). The label will include instructions to shake the suspension prior to administration.

7.3 Preparation, Administration, and Dosage of Study Drug

Subjects will be given two doses per day of an oral orange flavored suspension of either D-methionine or placebo daily starting three days prior to weapons training, for 11 days during weapons training, and an additional 4 days after completion of weapons training for total of 18 days administration. The total daily dose of D-methionine will not exceed 100 mg/kg per day.

Each subject's dose of D-methionine will be individually determined based on actual subject weight. For ease of administration and packaging, dosing is broken down by weight categories with dosing based on the lowest weight in that category as follows:

| Body Weight lbs (kg) | Total Daily Dose (Up to 100 mg/kg/day) |
|-----------------------------|---|
| 100-125 lbs (45 - 57 kg) | 4.6 grams (4600 mg) |
| 126-150 lbs (57 - 68 kg) | 5.6 grams (5600 mg) |
| 151-175 lbs (68 - 80 kg) | 6.8 grams (6800 mg) |
| 176-200 lbs (80 - 91 kg) | 8.0 grams (8000 mg) |
| 201-225 lbs (91 - 102 kg) | 9.2 grams (9200 mg) |

For example, if subject's body weight is 155 lbs (70.4 kg) then the subject's total daily dose equals 6.8 grams per day. This dose will be divided into two equal doses (3.4 grams) and administered prior to morning and evening meal (approximately 12 hours apart). Each dose (AM and PM) will be packaged in individually labeled vials by KP Pharmaceuticals.

KPT will assign the appropriate randomization code and prepare individualized doses of study drug prior to shipping to the Moncrief Army Community Hospital (MACH) Pharmacy at FT Jackson.

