| TREATMENTS | 
Two doses per day of an orange-flavored oral suspension (D-methionine or placebo) starting 3 days prior to weapons training, 11 days during weapons training, and 4 days after completion of weapons training. The total daily dose of D-methionine is up to 100 mg/kg fractionated into 2 doses of 50 mg/kg each.
 |
| MAIN PARAMETERS OF EFFICACY | 
Primary endpoint is to confirm safety and tolerability of up to 100 mg/kg daily given in divided doses approximately 12 hours apart.
 
Primary efficacy endpoint is change from baseline in pure-tone threshold as measured by absolute change and frequency of significant noise-induced threshold shift (STS).
 
Secondary efficacy endpoint is change from baseline scores for the tinnitus scales for both loudness and annoyance.
 |
| MAIN PARAMETERS OF SAFETY | 
Adverse event assessments will be made by study coordinator(s) as study drug is dispensed (twice daily) and at the end of the study.
 
Adverse events will be summarized by treatment group according to the last treatment taken before the Adverse Event (AE) began.
 |
| STOPPING RULES | 
Adverse event resulting in death, emergency surgery, or permanent and irreversible disability, unless determined unrelated to study participation. If an unexpected adverse event occurs in more than 3 subjects, then the risk of the active drug will be compared against risk of the placebo. Significantly higher rates in the active study group, based on severity of the adverse event, could warrant stopping trial.
 |
| DATA MONITORING | 
An on-site research monitor and an off-site medical monitor are assigned to this protocol. The project director, principal investigator, medical monitors, coordinator(s) and data manager of this protocol will schedule regular meetings via video or telephone conference to review study progress and safety data. The regulatory representative will also attend as needed, via teleconference, to determine if there are regulatory concerns or issues to handle based on the meeting content and outcome.
 |

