| STATISTICAL ANALYSIS | 
To confirm that the total daily dose of D-methionine 100mg/kg fractionated into 2 doses of 50 mg/kg each is safe and tolerable.
 
To determine if there is significantly reduced change in threshold hearing in each ear, adjusting for handedness, for the D-methionine group as compared to the placebo group at the tested audiometric frequencies.
 
To determine if there is a significantly lower rate of STS (in either ear) for the D-methionine group compared to the placebo group.
 
To determine if there is a significant difference in reported level of tinnitus between the D-methionine and the placebo groups.
 |

Clinical Trial Schema

List of Abbreviations

| | |
|----------|---|
| AAA | American Academy of Audiology |
| ACE-Mg | ACE-Magnesium |
| ADR | Adverse Drug Reaction |
| AE | Adverse Event/Adverse Experience |
| ANSI | American National Standards Institute |
| CCR | Center for Clinical Research |
| CFR | Code of Federal Regulations |
| COI | Conflict of Interest |
| CONSORT | Consolidated Standards of Reporting Trials |
| CRF | Case Report Form |
| DDEAMC | Dwight D. Eisenhower Army Medical Center |
| D-met | D-methionine |
| DFMO | Difluoromethylornithine |
| DHHS | Department of Health and Human Services |
| DOEHRSHC | Defense Occupational Environmental Health Readiness System-Hearing Conservation |
| DSM | Data and Safety Monitoring |
| FDA | Food and Drug Administration |
| FWA | Federal Wide Assurance |
| GCP | Good Clinical Practice |
| GSH | Glutathione |
| GSSG | Oxidized Glutathione |
| HIPAA | Health Insurance Portability and Accountability Act |
| IB | Investigator's Brochure |
| ICF | Informed Consent Form |
| IDE | Investigational Device Exemption |
| IND | Investigational New Drug |
| IRB | Institutional Review Board |
| ISM | Independent Safety Monitor |
| JC | Joint Commission |
| MACH | Moncrief Army Community Hospital |
| MCRD | Marine Corps Recruit Depot |
| N | Number (typically refers to participants) |
| NAC | N-acetylcysteine |
| NB | Narrow Band |
| NIHL | Noise Induced Hearing Loss |
| NCI | National Cancer Institute, NIH |
| NIH | National Institutes of Health |
| PI | Principal Investigator |
| PK | Pharmacokinetics |
| PTA | Pure Tone Average |
| QA | Quality Assurance |
| QC | Quality Control |
| SAE | Serious Adverse Event |
| SOP | Site Operations Manual |
| STS | Significant Noise-Induced Threshold Shifts |
| WHO | World Health Organization |

Definitions

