4.2 Study Endpoints

4.2.1 Primary Endpoints

- The first primary endpoint is to confirm safety and tolerability of administering up to 100 mg/kg daily, given in divided doses, twice daily (with morning and evening meal). The other primary efficacy endpoint is change from baseline in pure-tone thresholds as measured by absolute change and frequency of significant noise-induced threshold shift (STS).

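### Section 7.3 dose table: 4.6 g at 100 lb and 9.2 g at 201 lb slightly exceed the protocol's own 100 mg/kg/day cap (minor)

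*Combined protocol and SAP*

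**What the plan says.** Section 7.3 sets a ceiling: "The total daily dose of D-methionine will not exceed 100 mg/kg per day". Section 11.1 repeats it. Section 7.3 also gives the banding rule, "dosing based on the lowest weight in that category as follows", and a five-row table. The two rows at issue are "100-125 lbs (45 - 57 kg) | 4.6 grams (4600 mg" and "201-225 lbs (91 - 102 kg) | 9.2 grams (9200 mg". The other rows are 5.6 g from 126 lb (57 kg), 6.8 g from 151 lb (68 kg) and 8.0 g from 176 lb (80 kg).

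Each daily dose is split into two equal vials filled by the manufacturer. On strength, section 7.1 says: "The suspension is provided in small vials at a D-methionine concentration of 200 mg/mL".

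**The concern.** If each band is dosed from its lightest member, that member should receive at most 100 mg/kg and everyone heavier should receive less. In the first and last bands the lightest members receive more than the cap. For a soldier at either floor, site staff cannot follow both the table and the sentence above it. Because the manufacturer fills vials from the table, these are operative figures and not background text. What is at stake is agreement between the stated maximum dose and the dose dispensed.

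**Working it through.** **Inputs.** Cap, band floors (lb and printed kg) and doses, all from section 7.3. The documents name no conversion factor, so I tried the exact factor (0.45359237 kg/lb), 2.2 lb/kg, 2.205 lb/kg, 0.454 kg/lb and the kilograms printed in the table. The section's worked example, 155 lb = 70.4 kg, fits 0.454 best (155 × 0.454 = 70.37; exact gives 70.31; 155 / 2.2 gives 70.45).

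**Reproducing the plan's figures.** 100 mg/kg × 68 kg = 6,800 mg and 100 × 80 kg = 8,000 mg, as printed. The same rule on the other printed floors gives 4,500 mg (45 kg), 5,700 mg (57 kg) and 9,100 mg (91 kg), against printed values of 4,600, 5,600 and 9,200 mg. So two rows match, one is 100 mg below the rule, and two are 100 mg above it.

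**Dose at the band floor.** Formula: printed mg / floor weight in kg. For example, 4,600 / (100 × 0.45359237) = 4,600 / 45.36 = 101.41 mg/kg.

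| Floor (printed kg) | Dose, mg | Exact | 2.2 lb/kg | 2.205 lb/kg | × 0.454 | Printed kg |
|---|---|---|---|---|---|---|
| 100 lb (45) | 4,600 | 101.41 | 101.20 | 101.43 | 101.32 | 102.22 |
| 126 lb (57) | 5,600 | 97.98 | 97.78 | 98.00 | 97.90 | 98.25 |
| 151 lb (68) | 6,800 | 99.28 | 99.07 | 99.30 | 99.19 | 100.00 |
| 176 lb (80) | 8,000 | 100.21 | 100.00 | 100.23 | 100.12 | 100.00 |
| 201 lb (91) | 9,200 | 100.91 | 100.70 | 100.93 | 100.82 | 101.10 |

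The first and last rows exceed 100 in every column. The 176 lb row is at the cap in two columns and 0.1 to 0.2% over in three. The 126 lb and 151 lb rows never exceed it. A rough factor of 0.45 kg/lb, which I do not count as standard, raises the first and last rows to 102.22 and 101.71.

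**Size in milligrams.** Cap at the floor, exact: 100 × 45.36 = 4,536 mg and 100 × 91.17 = 9,117 mg. The excess is 4,600 − 4,536 = 64 mg/day and 9,200 − 9,117 = 83 mg/day. On the printed kilograms it is 100 mg/day in each band.

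**Where the excess ends.** 4,600 mg equals 100 mg/kg at 46 kg, which is 46 / 0.45359237 = 101.4 lb. 9,200 mg does so at 92 kg, or 202.8 lb. In whole pounds, only 100, 101, 201 and 202 lb are over the cap in these two bands. For 8,000 mg the exact-factor limit is 80 kg, or 176.4 lb.

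**Rest of each band.** At the band tops (exact factor) the doses run from 4,600 / 56.70 = 81.1 mg/kg at 125 lb to 9,200 / 102.06 = 90.1 mg/kg at 225 lb.

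**The case against.** The strongest reply is that this is rounding. If the floors were rounded up to 46 kg and 92 kg, both doses would be exactly 100 mg/kg. But the table prints 45 and 91 kg, and rounding up does not reproduce the 5.6 g or 6.8 g rows. Wording that allows doses up to the cap does not help either, because these doses are above it.

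A second reply is that all five printed doses halve to whole tenths of a gram, and section 7.3 gives ease of administration and packaging as the reason for bands. That stands as a constraint on the remedy. A rounding tolerance on the cap would leave the vials unchanged, but it would relax a limit the protocol states more than once.

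Third, the discrepancy is very small. That stands in full.

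Stronger readings are tempting, and the documents do not support them:

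- A reader might infer that the table also breaks the lowest-weight rule. Section 7.3 does not say that the dose is exactly 100 mg/kg times the floor, and 5.6 g departs from that product too. Only the cap is clearly contradicted.
- A reader might infer that 8.0 g is plainly wrong as well, or that it fails only with the exact factor. It is at the cap under 2.2 lb/kg or the printed 80 kg, and just over it under the exact factor, 0.454 and 2.205.
- A reader might infer general overdosing. Most of each band lies below the cap.
- A reader might infer from the synopsis Statistical Analysis entry, "To confirm that the total daily dose of D-methionine 100mg/kg fractionated into 2 doses of 50 mg/kg each is safe and tolerable", that a fixed 100 mg/kg is under test. Section 4.2.1 ("confirm safety and tolerability of administering up to 100 mg/kg daily, given in divided doses") and the synopsis Treatments entry ("The total daily dose of D-methionine is up to 100 mg/kg fractionated into 2 doses of 50 mg/kg each") show that it is a ceiling. The missing *up to* is an editorial note and changes no dose, endpoint or analysis.

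**Conclusion.** The point holds and is minor. The 4.6 g and 9.2 g entries contradict the 100 mg/kg/day cap at their band floors, by 1.2 to 2.2% at 100 lb and 0.7 to 1.1% at 201 lb across the conversions in the table. The excess is confined to roughly the lowest 1.4 lb and 1.8 lb of those bands. The 8.0 g entry is borderline and needs a stated convention more than a correction.

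The conclusion rests on reading the cap as a strict limit and on the band floors as printed. The documents give no weight distribution, so the number of soldiers affected is unknown and could be zero. No effect on safety, power or the treatment comparison is claimed, and nothing in the documents would support one.

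**What to change.** For classes not yet dosed:

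- Change 4.6 g to 4.5 g and 9.2 g to 9.1 g. The floors become 99.2 and 99.8 mg/kg (exact), 99.0 and 99.6 (2.2 lb/kg), and 100.0 in both bands on the printed kilograms.
- If half-doses must be whole tenths of a gram, use 4.4 g and 9.0 g instead (halves 2.2 g and 4.5 g).
- Leave 5.6 g, 6.8 g and the cap unchanged.
- For 176 to 200 lb, either lower 8.0 g to 7.9 g or state that floors are taken in whole kilograms as printed, so that 8.0 g equals the cap.

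Cost: the daily dose falls by 0.1 / 4.6 = 2.2% and 0.1 / 9.2 = 1.1% in the two bands (4.3% and 2.2% with 4.4 g and 9.0 g), and by 0.1 / 8.0 = 1.3% in the 176 lb band if 7.9 g is chosen. Half-doses become 2.25 g and 4.55 g (and 3.95 g with 7.9 g), which is slightly awkward. At 200 mg/mL each affected fill falls by 0.25 mL, from 11.5 to 11.25 mL and from 23 to 22.75 mL (and from 20 to 19.75 mL with 7.9 g). Earlier classes will have been dosed on the old table, so the study report should record both tables and the date of change.

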7.4 Study Drug Storage

All study drug will be stored under conditions consistent with package labeling (15-30 ° C; 59-86 ° F). All study drug will be stored in a secure limited-access area under controlled temperature in accordance with labeled storage requirements. Refrigeration is not required. Room temperature will be monitored and recorded daily, including weekends and holidays.

Shelf life at Ft. Jackson is not an issue because the study drug will arrive one week prior to the administration to each study participant and will only be dispensed over an 18 day period thereafter.

7.5 Study Product Accountability Procedures

Upon receipt of study drug, the MACH Pharmacist will ensure that the information on the packing slips matches exactly with information sent to the site, including content, amount, lot numbers, quantity, and expiration date.

The study coordinator(s) will also maintain accurate records of all study drug. In addition, accurate records will be kept regarding when and how much of each study drug is dispensed and used by each subject. This information will be recorded in each subject's EHR and on their medication log.

7.6 Assessment of Participant Compliance with Study Drug

Subject compliance will be determined by reconciliation of the subject's daily dosing regimen against the medication log.

7.7 Concomitant Medications and Procedures

All other medications taken by the subject during the study period will be recorded. Information will include: drug, dose, route of administration, start and end dates and indication.

7.8 Prohibited Medications and Procedures

Treatment with intravenous (IV) antibiotics, such as Amikacin: Amikin®, Gentamicin, Netilmicin: Netromycin®, Streptomycin, Tobramycin: Nebcin® or any other aminoglycosides and/or vancomycin. Also, any surgical or medical condition that might significantly alter the absorption, distribution, metabolism, or excretion of any drug. Subjects who received treatment for drug or alcohol abuse within the previous 6 months are prohibited from participation in this study.

7.9 Dietary Information (Daily Protein Intake)

Daily dietary information is available from Ft Jackson to ensure that adequate protein is available in the participant's daily diet.

7.10 D-methionine Antidote

The toxicity of methionine can be alleviated by dietary supplementation with glycine (Benevega and Harper 1967; Benevega 1974). However, these studies were conducted with L-methionine in animals.

8.0 ASSESSMENTS OF SAFETY

8.1 Safety Parameters

Safety and tolerability will be determined by evaluating any treatment emergent adverse events or change in baseline concomitant medications.

8.2 Definition of an Adverse Event (AE)

An adverse event (AE) is any unanticipated or unintended medical occurrence or worsening of a sign or symptom (including an abnormal laboratory finding) or disease in a study participant, which does not necessarily have a causal relationship with the study condition, procedures or study agent(s), that occurs after the informed consent is obtained.

Pre-existing conditions or illnesses, which are expected to exacerbate or worsen, are not considered adverse events and will be accounted for in the subject's medical history.

8.3 Definition of a Serious Adverse Event (SAE)

A Serious Adverse Event (SAE) is defined as an AE meeting one of the following outcomes:

- Death during the period of protocol defined surveillance
- Life Threatening Event (defined as a participant at immediate risk of death at the time of the event)
- Inpatient hospitalization or prolongation of existing hospitalization during the period of protocol defined surveillance
- Results in congenital anomaly or birth defect
- Results in a persistent or significant disability/incapacity

Any other important medical event that may not result in one of the above outcomes, may be considered a serious adverse event when, based upon appropriate medical judgment, the event may jeopardize the participant and may require medical or surgical intervention to prevent one of the outcomes listed above. Examples of such medical events include allergic bronchospasm requiring intensive treatment in an emergency room or at home, blood dyscrasias or convulsions that do not result in inpatient hospitalization, or the development of drug dependency or drug abuse.

8.4 Methods and Timing for Assessing, Recording, Analyzing, and Managing Safety Parameters

8.4.1 Assessment of Safety

General health status and symptom assessments performed at Baseline/Eligibility Visit and Study Visit 1 will serve as baseline for any new signs or symptoms that arise during the study. All such changes occurring after Study Visit 1 will be evaluated as possible adverse events and appropriately recorded on the Adverse Event Case Report Form (CRF).

Baseline and Study Visit 1 assessments are limited to general health history information, pregnancy testing and laboratory assessment for kidney function. Additional safety assessments have been added to include: laboratory evaluations (hematology, blood chemistry, and urinalysis) at pre-specified time points (e.g., pre-treatment, during treatment, and post-treatment). Expected adverse events include possible gastrointestinal (GI) symptoms (nausea, vomiting, constipation, diarrhea, dysphagia).

Subjects will be questioned prior to receiving each study dose and on the last study day for the presence of GI side effects. *See Estimating Severity Grade and method for classifying GI adverse events. Other subject reported symptoms that occur between Study Day 1 and Study Day 18, including the follow up visit at Study Day 29 - 32, will be evaluated as a possible adverse event. If a subject experiences a side effect that requires additional medical attention, the subject will seek medical attention through appropriate standard operating sick call procedures and the medical monitor will be contacted.

Adverse events will be evaluated according to the Estimating Severity Grade and will be recorded on the Adverse Event Log and the Adverse Event CRF. Adverse events deemed greater than Grade 2 will be considered a Serious Adverse Event (SAE). All SAEs will be recorded on the SAE CRF and reported according to FDA and institutional requirements (See Section 8.5 – Specific Serious Adverse Event Reporting Requirements).

Compliance and adverse event reports will be obtained each day that study drug is administered (Study Days 1-18) and at the end of the study (Study Day 29 -32) by the Study Coordinator(s). Each adverse event will be graded according to the Table for Estimating Severity Grade.

For all subjects receiving at least one dose of study drug, the number and percentage of subjects reporting adverse events will be tabulated by cohort and overall by severity and body system.

| ESTIMATING SEVERITY GRADE | | | | |
|----------------------------------|---|--|---|--|
| Grade 1 (Mild) | Event requires minimal or no treatment and does not interfere with the subject's daily activities | | | |
| Grade 2 (Moderate) | Event results in a low level of inconvenience or concern with the therapeutic measures. Moderate events may cause some interference with functioning. | | | |
| Grade 3 (Severe) | Event interrupts a patient's usual daily activity and may require systemic drug therapy or other treatment. Severe events are usually incapacitating. | | | |
| Grade 4 (Life-Threatening) | Any adverse drug experience that places the patient or participant, in the view of the investigator, at immediate risk of death from the reaction as it occurred, i.e., it does not include a reaction that had it occurred in a more severe form, might have caused death. | | | |
| Grade 5 | Death | | | |
| GASTROINTESTINAL | | | | |
| | Grade 1 | Grade 2 | Grade 3 | Grade 4 |
| Nausea | Mild or transient; maintains reasonable intake | Moderate discomfort; intake decreased significantly; some activity limited | No significant intake; requires IV fluids | Hospitalization required |
| Vomiting | 1 episode in 24 hours | 2-5 episodes in 24 hours | > 6 episodes in 24 hours or needing IV fluids | Physiological consequences requiring hospitalization or requiring parenteral nutrition |
| Constipation | Requiring stool softener or dietary modification | Requiring laxatives | Obstipation requiring manual evacuation or enema | Obstruction or toxic megacolon |
| Diarrhea | Mild or transient; 3-4 loose stools/day or mild diarrhea lasting for less than 1 week | Moderate or persistent; 5-7 loose stools/day or diarrhea lasting > 1 week | > 7 loose stools/day or bloody diarrhea; or orthostatic hypotension or electrolyte imbalance or > 2L IV fluids required | Hypotensive shock or physiological consequences requiring hospitalization |
| Oral discomfort/dysphagia | Mild discomfort; no difficulty swallowing | Some limits on eating/drinking | Eating/talking very limited; unable to swallow solid foods | Unable to drink fluids; requires IV fluids |

All AEs will be reviewed by the Medical Monitor (see Section 8.6) and the Data Safety Monitoring Committee (DSMC). The medical monitor will discuss each adverse event and determine causality in consultation with the Principal Investigator. The degree of certainty about causality will be graded using the categories below:

- **Definitely Related:** There is clear evidence to suggest a causal relationship, and other possible contributing factors can be ruled out. The clinical event occurs in a plausible time relationship to drug administration and cannot be explained by concurrent disease or other drugs or chemicals. The response to withdrawal of the drug should be clinically plausible.
- **Probably Related:** There is evidence to suggest a causal relationship, and the influence of other factors is unlikely. The clinical event occurs within a reasonable time sequence to administration of the drug, is unlikely to be attributed to concurrent disease or other drugs or chemicals.
- **Possibly Related:** There is some evidence to suggest a causal relationship (e.g., the event occurred within a reasonable time after administration of the trial medication). However, the influence of other factors may have contributed to the event (e.g., the subject's clinical condition, other concomitant events). Although an adverse drug event may rate only as "possibly related" soon after discovery, it can be flagged as requiring more information and later be upgraded to "probably related" or "definitely related", as appropriate.
- **Unlikely:** A clinical event whose temporal relationship to drug administration makes a causal relationship improbable (e.g., the event did not occur within a reasonable time after administration of the trial medication) and in which other drugs or chemicals or underlying disease provides plausible explanations (e.g., the subject's clinical condition, other concomitant treatments).
- **Unrelated:** The AE is completely independent of study drug administration, and/or evidence exists that the event is definitely related to another etiology. There must be an alternative, definitive etiology documented by the clinician.
- **Expected Events Related to Disease Process:** Expectedness refers to the awareness of adverse events previously observed, not on the basis of what might be anticipated from the pharmacological properties of the study agent.

Subjects will be questioned by the on-site study coordinator(s) prior to receiving each study dose and on the last study day for the presence of side effects or adverse experiences. If an event is reported, the following questions will be asked of the subjects and recorded by the on-site study coordinator(s):

- Onset of event
- Duration of event
- Intensity of event
- Relationship to study medication

Each subject's baseline data (pre-noise exposure) will act as their own control. Any side effects reported after receiving the first dose will be recorded (with answers to the aforementioned questions). At study completion, any new occurrence of a side effect or an increase in intensity of a pre-existing event will be recorded. If a subject experiences a side effect that warrants additional medical attention, the subject will seek medical attention through appropriate standard operating sick call procedures and the medical monitor will be contacted and it will be entered on the CRF.

Side effects will be compared within subjects, as well as between treatment groups (D-methionine and placebo) for onset, duration, frequency and relationship to treatment. These comparisons will be made for side effects present at baseline, and for those that occurred during and after completion of treatment.

